6.4.2 Physical Examination

A full physical examination is performed at the Screening and Week 12 / Early Termination visits, and will include assessments of the following body systems: General Appearance; HEENT; Cardiovascular; Respiratory; Gastrointestinal; Dermatological; Neurological; Musculoskeletal; Lymphatic; and Other.

The number and percentage of subjects with normal, abnormal not clinically significant and abnormal clinically significant results respectively will be summarized for each body system at each visit by treatment group and overall.

6.4.3 Vital Signs

Vital signs measurements are taken at the Screening and Week 12 / Early Termination visits. Vital signs collected will include systolic and diastolic blood pressures (millimeters of mercury (mmHg)) and heart rate (beats per minute) recorded after the subject has been seated for 5 minutes, height (cm) [at Screening only] and weight (kg).

Body Mass Index (BMI) will be derived at each visit as:

$$\frac{\text{Weight (kg)}}{[\text{Height (cm)} / 100]^2}$$

The absolute values of systolic blood pressure, diastolic blood pressure, heart rate, height, weight and BMI will be summarized at each visit by treatment group and overall, using summary statistics for continuous variables. Change from Baseline (Screening) values will also be summarized for systolic blood pressure, diastolic blood pressure, heart rate and weight at the Week 12 / Early Termination visit.

6.4.4 Electrocardiogram

Two 12-lead ECG examinations will be performed approximately 5 minutes apart from one another at each of the Screening and Week 12 / Early Termination visits. The ECG vendor, [REDACTED], will provide the following interval measurements for each ECG: Ventricular Rate (beats per minute); PR Interval (msec); RR Interval (msec); QRS Interval (msec); QT Interval (msec); QT Interval corrected according to Bazett Formula (QTcB, msec); and QT Interval corrected according to Fridericia Formula (QTcF, msec). The ECG vendor will also provide an overall interpretation of each ECG (normal, abnormal not clinically significant or abnormal clinically significant).

For each of the interval measurements, the mean of the two results at each visit will be evaluated for each subject to represent the overall result at that visit. If only one result is available for a given parameter at a particular visit, then that result will be used to represent the overall result for that parameter at that visit.

For the overall interpretation, the worst of the two results at each visit will represent the overall interpretation at that visit (where abnormal clinically significant represents the worst result, followed by abnormal not clinically significant and normal respectively). If only one overall interpretation is available at a particular visit, then that result will be used to represent the overall interpretation at that visit.

The absolute values of each interval measurement (ventricular rate, PR, RR, QRS, QT, QTcB and QTcF) will be summarized at each visit by treatment group and overall, using summary statistics for continuous variables. Change from Baseline (Screening) values will also be summarized for the Week 12 / Early Termination visit, along with the 95% CI for the mean change from Baseline.

The number and percentage of subjects with normal, abnormal not clinically significant and abnormal clinically significant overall interpretations respectively will be summarized at each visit by treatment group and overall.

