3.1.1 Rationale of Study Design

The study design is concordant with a dose response approach (three doses of estrogens will be tested and compared to placebo), as well as the indication and the estrogenic nature of the product, and thus follows the recommendations of the FDA in Draft Jan 2003 Recommendations for Clinical Evaluation of Estrogen/Progestins to Treat Vulvovaginal Symptoms.

A placebo arm has been included in the study as per the above referenced FDA recommendations, in which it is indicated to demonstrate a statistically significant improvement versus placebo in the primary efficacy analyses. By selecting placebo as comparator, all potential influences on the actual or apparent course of the disease other than those arising from the pharmacologic action of the test drug are controlled. Placebo-controlled trials measure the total pharmacologically mediated effect of treatment, and provide the maximum ability to distinguish adverse effects caused by a drug from those resulting from underlying disease or intercurrent illness. (ICH Guideline E10)

4 Subject Selection and Withdrawal Criteria

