7.4 Safety Endpoints

The following safety variables will be analyzed:

- laboratory parameters
 - biochemistry, hematology and urinalysis at Week 12;
 - serum lipids, and coagulation parameters at Week 12;
 - change from Baseline in hormone levels (estradiol, estrone, estriol, FSH, LH);

- change from Baseline in uterine evaluation by transvaginal ultrasound at Week 12 for women with an intact uterus;
- change from Baseline in endometrial histology at Week 12 for women with an intact uterus;
- frequency and severity of AEs;
- change from Baseline in ECG QTc

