7.8.4 Safety Analyses

The assessment of safety will be based on the incidence of AEs occurring during the 12-weeks on study treatment, and changes from Baseline to Week 12 in laboratory values and ECG QTc determinations. Changes from Baseline to Week 12 in transvaginal ultrasound findings will be summarized for women with an intact uterus. Changes in endometrial histological evaluation at Week 12 will be summarized for women with an intact uterus.

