7. TABLES, LISTINGS, AND FIGURES

The general layout of the tables, listings and figures will be as follows:

Orientation	Landscape
Paper Size	A4
Margins	Top: 3.2 cm Bottom: 2.5 cm Left: 2.5 cm Right: 2.5 cm
Font	Courier New 8 point
Headers (alignment)	Sponsor name and Protocol number (Left) Page X of Y (Right) Table/Listing/Figure Number and Title (Centre)
Footers (alignment)	SAS program path and file name (Left) Date output generated (Right)

The font size may be reduced as necessary to allow additional columns to be presented, but not at the expense of clarity. Also, the orientation may be changed to portrait, if appropriate.

The date format for all presentations will be 'DDMMYY YYYY'.

All statistical analysis will be performed using SAS® Version 9.3 or higher for Windows.

The treatment labels for all outputs will be as shown in **Table 6**.

Table 6: Treatment Labels for Statistical Outputs

0.005% Estriol
0.002% Estriol
0.008% Estriol
Placebo
Total (Tables only)

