Table 14.3.5.2	Summary of Shifts from Baseline to Week 12 / Early Termination for Transvaginal Ultrasound Assessments	Safety Population
Table 14.3.6.1	Summary of Endometrial Biopsy Histologic Characteristics by Treatment and Visit	Safety Population
Table 14.3.6.2	Summary of Shifts from Baseline to Week 12 / Early Termination for Endometrial Biopsy Histologic Characteristics	Safety Population
Table 14.3.7.1	Summary of 12-Lead Electrocardiogram Parameters by Treatment and Visit	Safety Population
Table 14.3.7.2	Summary of 12-Lead Electrocardiogram Overall Interpretation by Treatment and Visit	Safety Population
Table 14.3.8	Summary of Vital Signs by Treatment and Visit	Safety Population
Table 14.3.9	Summary of Physical Examination by Treatment and Visit	Safety Population
Table 14.3.10	Summary of Gynecological Examination by Treatment and Visit	Safety Population

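### The only interval planned for the QTc safety endpoint is a by-group 95% CI for mean change; no estriol-minus-placebo difference or interval is planned

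*SAP*

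**What the plan says.** Protocol 7.4 lists "change from Baseline in ECG QTc" among the safety variables. Protocol 7.8.4 rests the safety assessment partly on "changes from Baseline to Week 12 in laboratory values and ECG QTc determinations" and names no comparison.

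SAP 6.4.4 averages the two ECGs taken at each visit. It says that the interval measurements, including QTcB and QTcF, "will be summarized at each visit by treatment group and overall, using summary statistics for continuous variables". It then adds: "Change from Baseline (Screening) values will also be summarized for the Week 12 / Early Termination visit, along with the 95% CI for the mean change". SAP 7.2.3 lists two ECG tables. The one carrying these values is Table 14.3.7.1, "Summary of 12-Lead Electrocardiogram Parameters by Treatment and Visit"; the other covers overall interpretation. Neither is a table of differences.

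Placebo is one of the displayed groups: "The treatment labels for all outputs will be as shown in Table 6", and that table includes Placebo and a Total.

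Protocol 3.1.1 justifies the placebo arm partly on safety grounds, saying that such trials "provide the maximum ability to distinguish adverse effects caused by a drug from those resulting from underlying disease or intercurrent illness".

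**The concern.** A confidence interval for the mean change in one arm says how precisely the movement between Screening and Week 12 has been measured in that arm. It does not say how much of that movement is due to estriol, because nothing is subtracted for whatever would have happened on placebo. In a randomized placebo-controlled trial, the drug effect on QTc is the difference in mean change between a dose and placebo, and that quantity has no planned estimate or interval.

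This is more than a routine descriptive gap, for two reasons. Among the safety analyses in SAP 6.4, ECG change is the only item given a confidence interval; vital signs and laboratory values get descriptive change only. The plan thus chose to express uncertainty for ECG change but attached it to a quantity that does not isolate the drug. Also, SAP 6.3.1.2 and 6.3.1.3 already plan the appropriate form for pH and cytology: least-squares mean differences from placebo with 95% CI.

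At stake is the statement the study report can make about estriol and QTc. Without the difference, a reader has to compare separate intervals by eye. That can suggest an effect that is absent or obscure one that is present.

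**Working it through.** **Inputs from the documents.** Allocation is 1:1:1:1. The sample size is 57 evaluable per group, set for vaginal dryness and not for QTc, inflated for 18% drop-out (SAP 6.1.4). Check: 57 / (1 − 0.18) = 69.5, so 70 per group and 4 × 70 = 280, as stated. A simulation of the Wilcoxon test with the proportions in SAP Table 2 gives 90.4% power at 57 per group, so the plan's 90% also reproduces. Missing safety data are not imputed (SAP 6.4), so the number with QTc change should lie between about 57 and 70 per arm.

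**Assumed, because the documents give no figure.** SD of QTc change 15 msec, range 10 to 20, equal across arms. Any shift or drug effect used below is illustrative.

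**Half-widths.** By group: t(n−1) × SD / √n. Difference from placebo, unadjusted: t(2n−2) × SD × √(2/n). For n = 57 and SD 15:
- by group: 2.003 × 15 / √57 = 3.98 msec
- difference: 1.981 × 15 × √(2/57) = 5.57 msec
- ratio: 5.57 / 3.98 = 1.40

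| n per arm | SD (msec) | By-group half-width | Difference half-width |
|---|---|---|---|
| 57 | 10 | 2.7 | 3.7 |
| 57 | 15 | 4.0 | 5.6 |
| 57 | 20 | 5.3 | 7.4 |
| 70 | 10 | 2.4 | 3.3 |
| 70 | 15 | 3.6 | 5.0 |
| 70 | 20 | 4.8 | 6.7 |

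**Why comparison by eye is unreliable** (n = 57, SD 15):

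1. *Overlap.* Two by-group intervals stop overlapping only when the means differ by more than 2 × 3.98 = 7.96 msec. The difference interval excludes 0 once they differ by more than 5.57 msec. Between about 5.6 and 8.0 msec, overlapping intervals would suggest no difference although the direct interval excludes 0.
2. *Discordance.* Suppose every arm shifts by +3 msec and there is no drug effect. A by-group interval then lies wholly above 0 with probability 0.317 (noncentral t). A given dose's interval does so while placebo's does not with probability 0.317 × (1 − 0.317) = 0.22. The difference interval lies wholly above 0 with probability 0.025.
3. *Masking.* Suppose every arm shifts by −5 msec and a dose adds +5 msec. Centred on expected values, the dose's interval is 0 ± 4.0 (−4.0 to 4.0) and placebo's is −5 ± 4.0 (−9.0 to −1.0). Read alone, the dose appears to have no effect and an upper limit of 4.0 msec. The difference interval is 5 ± 5.6 (−0.6 to 10.6), which shows the drug effect and how large it could be.

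**The case against.** The strongest reply is that this is a descriptive safety table and does its job. There is no QTc hypothesis, margin or decision rule in either document. The interval correctly estimates what it names. Placebo stands beside each dose, and SAP 6.1.1 puts n, mean and SD in summary tables, so anyone can compute the unadjusted difference and its interval. Other safety data are also reported by arm without contrasts, and ECG already receives more than they do.

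Much of this stands. A reader might infer that any shift common to all arms would be taken for an estriol effect. The documents do not support that, because the same shift would appear in the placebo column of the same table. Nor are the probabilities in the working error rates of the plan: they apply a reading rule (interval wholly above 0, or one arm's interval against another's) that the SAP nowhere adopts, and nothing in the documents indicates that a shift will occur. The term by-group is itself an inference from the preceding sentence and the table title, though the natural one.

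The objection does not remove the gap. A contrast computed afterwards by a reader is post hoc and not adjusted for country or Baseline. The Total column does not help, because it pools three estriol arms with placebo.

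**Conclusion.** The point holds as a minor one. The one interval planned for a named safety endpoint does not estimate the drug effect, and the estimate that would do so is not planned, although the trial randomizes to placebo and the SAP uses that form for pH and cytology. Because placebo is displayed alongside, the consequence is a risk of misreading or masking rather than a built-in false conclusion.

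The size depends on assumption. With 57 to 70 evaluable per arm and an SD of change of 10 to 20 msec, the missing difference interval would have a half-width between 3.3 and 7.4 msec, about 5.6 msec at n = 57 and SD 15. The co-primary analyses, the gatekeeping procedure and the sample size are unaffected.

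**What to change.** Keep the by-group ECG summaries and their confidence intervals. In SAP 6.4.4 and Table 14.3.7.1, add for QTcF and QTcB change at Week 12 / Early Termination, in the Safety population, the difference of each estriol dose from placebo with a two-sided 95% CI. Obtain it from an ANCOVA of change on treatment, country and the Baseline (Screening) value. State that this is estimation without a hypothesis test, and that any statement about an estriol effect on QTc rests on this placebo-adjusted difference. This is 2 corrections × 3 doses = 6 contrasts; the other ECG intervals can stay descriptive.

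The cost is a short addition to SAP wording and one block in an existing table. The ECGs are already taken in every arm, so no visit, procedure or subject is added. The downside is precision: the unadjusted difference interval is about 1.4 times as wide as the by-group one. Baseline adjustment may narrow it somewhat, but the documents give no correlation from which to say by how much.

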6.4.5 Laboratory Parameters

Clinical laboratory tests will be performed under fasting conditions at the Screening and Week 12 / Early Termination visits. The following parameters will be assessed:

- Hematology:
 - Basophils
 - Eosinophils
 - Lymphocytes
 - Monocytes
 - Neutrophils
 - Basophils/Leukocytes
 - Eosinophils/Leukocytes
 - Lymphocytes/Leukocytes
 - Monocytes/Leukocytes
 - Neutrophils/Leukocytes
 - Hematocrit
 - Hemoglobin
 - Platelets
 - Erythrocytes
 - Leukocytes
 - Factor V Leiden (either at Screening or at Week 12 / Early Termination if not previously obtained at Screening)
- Blood Chemistry:
 - Albumin
 - Alanine Aminotransferase
 - Aspartate Aminotransferase
 - Blood Urea Nitrogen
 - Creatine Kinase
 - Creatinine
 - Glucose
 - Bilirubin
 - Protein
 - Urate
 - Triglycerides
 - Cholesterol
 - Cholesterol: High-Density Lipoprotein
 - Cholesterol: Low-Density Lipoprotein
- Urinalysis:
 - pH
 - Specific Gravity
 - Clarity
 - Colour
 - Protein
 - Glucose
 - Occult Blood

- Leukocytes – assessed routinely by dipstick; sediment method is used to confirm a positive dipstick result. If both dipstick and sediment results are present at the same visit, the sediment result will be used any applicable statistical summaries.
- Bilirubin
- Ketones
- Urobilinogen
- Nitrates
- Erythrocytes
- Bacteria
- Casts
- Crystals
- Epithelial Cells
- Yeast Cells
- Coagulation:
 - Activated Partial Thromboplastin Time
 - Prothrombin Time
 - Protein C
 - Protein S
 - Thrombin/Antithrombin III
 - Fibrinogen
- Endocrinology (Hormones):
 - Estradiol
 - Estriol
 - Estrone
 - Follicle Stimulating Hormone (FSH)
 - Luteinizing Hormone (LH)

The samples will be analyzed by the central laboratory, [REDACTED] Reference ranges are available for all applicable parameters in Appendix I of the [REDACTED] Laboratory Manual. All parameters will be summarized in conventional units as provided by [REDACTED]

The absolute values of continuous laboratory parameters will be summarized at each visit by treatment group and overall, using summary statistics for continuous variables. Change from Baseline (Screening) values will also be summarized at the Week 12 / Early Termination visit. Categorical laboratory parameters will be listed only.

Tables presenting the shift in result (low, normal, high) from Baseline (Screening) to Week 12 / Early Termination will also be presented for each laboratory parameter by treatment group. For the shift tables, the denominator of percentage will be the number of subjects in the Safety population in each treatment group.

6.4.6 Transvaginal Ultrasound

A transvaginal ultrasound is performed at the Screening and Week 12 / Early Termination visits for subjects with an intact uterus, and will include assessments of endometrial thickness and pelvic pathology (ovaries, miomas, etc.).

The number and percentage of subjects with normal, abnormal not clinically significant and abnormal clinically significant results, respectively, will be summarized for each assessment at each visit by treatment group and overall.

A table presenting the shift in result (normal, abnormal not clinically significant, abnormal clinically significant) from Baseline (Screening) to Week 12 / Early Termination visit will also be presented for each assessment by treatment group. For the shift table, the denominator of percentage will be the number of subjects in the Safety population in each treatment group.

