- If the woman has a uterus, perform transvaginal ultrasound to determine endometrial thickness and identify any gynecological abnormalities that would interfere with administration of the study drug, study procedures or results;
- If the woman has an intact uterus, an endometrial biopsy will be performed;
- Safety laboratory parameters (biochemistry and hematology, including coagulation and lipids, urinalysis) and serum hormone levels. These analysis should be performed under fasting conditions
- Report adverse events

The investigator or other qualified designee is to review information obtained to ensure subject meets all of the inclusion and none of the exclusion criteria for all measurements studied in the Screening Visit.

Before the Baseline Visit, the investigator will confirm that the subject meets all the inclusion and exclusion criteria, including the endometrial histological assessment.

Subjects with signs and symptoms suggestive of infection of the genital or urinary tract requiring treatment at the start of the study will be excluded. However, once treated and symptoms have resolved (or there are negative microbiology findings), subjects can be re-screened into the study. Refer to section 4.2.3 for more details.

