6.3.2 Transvaginal Ultrasound

Transvaginal ultrasound (TVU) will be performed by the investigator, sub-investigator or designated trained member of the staff at the Screening Visit to determine whether there are any abnormalities of the ovaries, whether the uterus and cervix are present, and whether there are any physical issues that would exclude the subject from participation in the study. In addition, TVU will be performed to measure endometrial thickness and to investigate the presence of any abnormal morphological findings. Follow-up TVU will be

conducted during the Week 12/Early Termination Visit, and any clinically significant changes from baseline will be noted.

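### Endometrial thickness is measured by ultrasound, but the SAP tabulates it only in three clinical-significance categories, so a dose-related change within normal would not show in any ultrasound table

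*SAP*

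**What the plan says.** The protocol describes thickness as something measured. At Screening, in women with a uterus, the site is to "perform transvaginal ultrasound to determine endometrial thickness" (Protocol 6.1.1). Protocol 6.3.2 repeats that "TVU will be performed to measure endometrial thickness". The scan is repeated: follow-up is "conducted during the Week 12/Early Termination Visit, and any clinically significant changes from baseline will be noted". The examination "will be performed by the investigator, sub-investigator or designated trained member of the staff"; no central reading is described.

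Protocol 7.4 lists as a safety endpoint the "change from Baseline in uterine evaluation by transvaginal ultrasound at Week 12 for women with an intact uterus". Protocol 7.8.4 adds: "Changes from Baseline to Week 12 in transvaginal ultrasound findings will be summarized for women with an intact uterus".

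SAP 6.4.6 confirms that the scan at both visits "will include assessments of endometrial thickness and pelvic pathology". Its summary is: "The number and percentage of subjects with normal, abnormal not clinically significant and abnormal clinically significant results, respectively, will be summarized for each assessment", by visit, treatment group and overall. A shift table uses the same three levels, with every Safety-population subject in the arm in the denominator. SAP 7.2.3 lists two ultrasound tables, 14.3.5.1 (by visit) and 14.3.5.2 (shifts), which match this text. No summary statistics for thickness are planned, and neither document gives a threshold for abnormal.

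**The concern.** This trial compares three doses of an estrogen with placebo, and Protocol section 1 names endometrial tumors among the main risks of estrogen after menopause. Whether thickness moves with dose is a natural safety question. If mean thickness rose with dose while nearly all women stayed within normal, both planned ultrasound tables would look flat.

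Three features weaken the category further. Without a stated cut-off, each reader decides what is abnormal. Readers are local staff at about 25 sites. The shift-table denominator includes women who had no scan because they have no uterus, so the percentages are diluted, by an amount that depends on how many such women each arm happens to contain.

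**Working it through.** **1. How the SAP treats other measured safety variables**

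| Variable | Continuous summary | Change from Baseline | Categorical summary |
|---|---|---|---|
| Laboratory, continuous parameters (SAP 6.4.5) | yes | yes | yes (shift table) |
| Blood pressure, heart rate, weight (SAP 6.4.3) | yes | yes | no |
| ECG intervals (SAP 6.4.4) | yes | yes, with 95% CI | yes (overall interpretation) |
| Endometrial thickness (SAP 6.4.6) | no | shift of category only | yes |

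Thickness is the exception. SAP 6.8, on changes from the protocol's methods, does not discuss it.

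**2. What the category loses: illustration on assumed inputs**

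The documents give no SD, expected effect, cut-off or power for thickness, so there is no plan figure to reproduce. Assumptions:

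- Thickness is normally distributed with equal SD in both arms.
- The estriol arm is shifted up by d = 0.5 SD.
- A share q of placebo women lies above the cut: 2%, 5%, 10% or 20%.
- The comparison is one-sided at 0.025 and the category is collapsed to two levels.
- n = 57 per arm, the evaluable number in Protocol 7.5 and SAP 6.1.4, as if all had a uterus.

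Measurement: power = Φ(d·√(n/2) − 1.96) = Φ(0.5 × √28.5 − 1.96) = Φ(2.669 − 1.96) = Φ(0.709) = 76%.

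Category: the same shift gives an estriol share p = 1 − Φ(z − d), where z is the 1 − q quantile. For q = 20%, z = 0.842 and p = 1 − Φ(0.342) = 36.6%. With a pooled variance under the null, power = Φ{[(p − q) − 1.96·√(2·m(1 − m)/n)] / √([q(1 − q) + p(1 − p)]/n)}, where m = (p + q)/2. For q = 20% this is Φ[(0.1663 − 0.1654)/0.0829] = 50%.

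| n per arm | Shift | Measurement | q = 2% | q = 5% | q = 10% | q = 20% |
|---|---|---|---|---|---|---|
| 70 | 0.5 SD | 84.1% | 22.6% | 35.4% | 47.5% | 59.0% |
| 57 | 0.5 SD | 76.1% | 19.2% | 29.8% | 40.1% | 50.4% |
| 34 | 0.5 SD | 54.0% | 13.1% | 19.5% | 25.9% | 32.8% |
| 57 | 0.3 SD | 36.0% | 9.0% | 12.7% | 16.7% | 21.2% |

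Seventy is the planned enrollment per arm; 34 assumes that 60% of 57 have a uterus. In every row the category has less power than the measurement for the same shift, and the gap is widest when few women are called abnormal.

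**3. The denominator**

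If 34 of 57 women have a uterus (assumed), one woman shifting to abnormal is 1/34 = 2.9% of those scanned but 1/57 = 1.8% in the planned table. Every percentage is multiplied by 34/57 = 0.60.

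**The case against.** **Is there a departure from the protocol?** A reader might infer one. The documents do not support that. Protocol 7.4 and 7.8.4 speak of change in the uterine evaluation and in ultrasound findings; neither requires millimeters. A Baseline-to-Week 12 shift table meets that wording, so SAP 6.8 had nothing to declare.

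**Are collected data thrown away?** A reader might infer this too, but it is not shown. The protocol says thickness is measured, yet for Week 12 it asks only that clinically significant changes be noted, and SAP 6.4.6 describes only a categorical result. Nothing shows a numeric eCRF field, and the table shells and listing layouts are not reproduced in the text. If millimeters are recorded, SAP 6.1.1 has all eCRF data listed, and Listing 16.2.9 covers ultrasound. What is missing is a between-arm summary.

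**Is endometrial safety left unprotected?** No. Biopsy is mandatory in women with a uterus at Screening and Week 12. Three blinded pathologists read the Week 12 slides (SAP 6.4.8), on a scale that distinguishes atrophic, inactive and several proliferative states below hyperplasia, and the result is tabulated by arm and as shifts. Sub-hyperplastic stimulation can therefore appear in planned tables. Nor do the documents say that thickness is the more sensitive measure. Biopsy can return no tissue or insufficient tissue (SAP Table 5, codes 0 and 1), so thickness still adds something.

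**Is power a fair yardstick?** Only as an illustration. SAP 6.4 plans no between-arm safety test, and every input is assumed. The figures compare two ways of summarizing one assumed shift; they are not a property of this trial.

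What stands after all this is that the planned tables are less informative than the measurement the protocol describes.

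**Conclusion.** The point holds as a minor improvement in safety reporting. The protocol describes a measured thickness with a repeat scan at Week 12; the SAP tabulates it only in three categories without a cut-off, and the shift table uses a denominator that includes women who are not scanned. A graded change within normal would be absent from both ultrasound tables.

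The size can only be illustrated: 76% power against 19% to 50% for a 0.5 SD shift with 57 women with a uterus per arm. This rests on normality, the assumed shares above the cut, and a two-level rather than three-level category. It also compares a single reading per woman and does not model change from Baseline or variation between local readers. The direction holds across the range tried; the exact figures should not be quoted as trial properties.

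Sample size, alpha, the four co-primary analyses and the minimal-effective-dose decision are untouched.

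**What to change.** 1. Confirm that endometrial thickness in millimeters is captured on the eCRF at Screening and at Week 12 / Early Termination. If it is not, add the field.
2. In SAP 6.4.6 and 7.2.3, add a table of thickness and change from Baseline by arm (n, mean, SD, median, quartiles, minimum, maximum), with a 95% CI for each estriol dose minus placebo, in women with a uterus and both readings. Keep it descriptive, without a test.
3. Keep the category shift table, but use women with a uterus in each arm as its denominator.

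The cost is one more descriptive table and possibly one data field. No procedure is added, because the scan is already scheduled at both visits. If the field is added after enrollment has begun, earlier readings would have to be retrieved from source records where they exist.
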